9.5.8. Follow-up of Adverse Events

During the study:

All AEs and SAEs must be followed-up during the study period until resolution or stabilisation.

After the end of the study, or at patient's premature discontinuation:

Only AEs or SAEs related to the study IMP that occurred during the study and:

- That are still recorded as “recovering”, “not recovered” or “worsening” at the end of the study, must be continuously followed-up as part of the study data, as long as necessary to adequately evaluate the patient’s safety, or until they are considered as “resolved”, or until the condition is stabilised, or until the Investigator no longer estimates that they are clinically significant. If resolved, a resolution date must be provided.

If a patient is withdrawn from the study due to safety reasons, she should be followed until the event disappears, is otherwise explained or the patient’s condition has stabilised.

Any patient who voluntarily withdraws from the study should be carefully questioned for the possible occurrence of an adverse event.

If no follow-up information can be provided, the Investigator must:

- Provide a written justification and
- Document the outcome as “unknown” (except for cases where the outcome is known, such as death for instance)

(Reminder: if the Investigator detects a new (S)AE after the end of the study and considers the event as possibly related to the IMP, he/she has to contact the Sponsor to determine how it should be documented and reported.)

Follow-up documentation

- In case of follow-up of an AE that worsened in nature or in severity, the follow-up will be documented on a new AE column in the CRF, with the box "follow-up" being ticked

- In case of follow-up of an SAE for which additional information/modification is provided, the follow-up will be reported on a new “SERIOUS ADVERSE EVENT FORM”, with the box "follow-up" being ticked

9.6. Regulatory Safety Requirements

The decision to notify SAEs to competent Authorities/Ethics Committee is under the responsibility of the Sponsor.

The Sponsor will ensure that the Investigators, and all other appropriate persons, are informed in a timely manner of findings that could adversely affect the safety of patients.

The Sponsor will communicate additional safety information, when available, to the appropriate Health Authorities/Ethics Committee and all Investigators.

10. PARAMETERS AND ASSESSMENT CRITERIA

10.1. Assessment of Efficacy

10.1.1. Primary Variable

The primary efficacy variable is a binary composite endpoint (failure versus success). Failure is defined when a patient loses at least 4 g/dL of Hb, and/or requires the transfusion of at least 2 units of RBCs within 48 hours following the administration of IMP.

The reference Hb level is the most recent Hb value recorded during the third trimester of pregnancy.

10.1.2. Secondary variables

The following efficacy criteria will be assessed by the investigators:

- Evolution of haemorrhage
 - Percentage of patients losing at least 4 g/dL of Hb, 48 hours following IMP administration with regards to the Hb reference level.
 - Percentage of patients losing at least 3 g/dL of Hb, 48 hours following the IMP administration with regards to the Hb reference level.
 - Percentage of patients requiring the transfusion of at least 2 units of packed RBCs, 48 hours following the IMP administration.
 - Percentage of patients losing at least 4 g/dL of Hb, 48 hours following the IMP administration with regards to the Hb level measured at inclusion.
 - Percentage of patients with an occurrence of Hb level < 9 g/dL within the 48 hours period following inclusion.
 - Number of units of transfused blood products within the 48 hours period following the IMP administration.
 - Calculated volume of total blood loss, 48 hours following the IMP administration.

The calculation and adjustment of total blood loss with regards to transfusional needs will be calculated at time of statistical analysis as follows:

- Total blood loss (mL) = blood loss calculated + blood loss compensated by transfusion
- Calculated blood loss: Pregnancy total blood volume x (Ht0 – Htf) x (100/35)
 - Pregnancy total blood volume = (Maternal weight measured before pregnancy x 65 mL/kg) x 1.4 (40,41)
 - Ht0: last available value of haematocrit before delivery
 - Htf: value of haematocrit in the morning of D2
- Blood loss compensated by transfusion (mL): n RBC x 500mL (with n corresponding to the number of transfused units and 500mL = total transfused blood volume of 300 mL RBC with Ht of 60%) (36)
- Need for haemostatic intervention
 - Percentage of patients requiring at least one of the following interventions within 48 hours following the administration of IMP: uterine ligation (B Lynch or other techniques), pelvic arteries embolization, surgical vascular ligation, administration of recombinant activated Factor VII (rFVIIa) and hysterectomy.
- Need for intrauterine balloon
 - Percentage of patients requiring the use of intrauterine balloon within 48 hours following the administration of IMP.
 - Time of intrauterine balloon placement.
- Maternal morbi-mortality
 - Length of stay in resuscitation and/or intensive care and/or PICU and/or continuous care
 - Length of stay in obstetrics units
 - Single or multi-organ failure (SOFA) score in women transferred to resuscitation and/or intensive care and/or PICU and/or continuous care units
 - Death during the study
- Evolution of blood fibrinogen level after early administration
 - Change in plasma fibrinogen level between H0 (start of IMP infusion) and D2.
- Evolution of hemoconcentration
 - Change in Hb level between each determination and H0
 - Change in Ht level between each determination and H0
 - Change in RBCs count between each determination and H0

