	
following the IMP administration, with regards to the level of Hb measured at inclusion.
 
 ○ Percentage of patients with an occurrence of Hb level < 9 g/dl within the 48 hours period following inclusion. ○ Number of units of transfused blood products within the 48 hours period following IMP administration. ○ Calculated volume of total blood loss, 48 hours following the IMP administration. 
 ● Need for haemostatic intervention 
 ○ Percentage of patients requiring at least one of the following interventions within 48 hours following the IMP administration: uterine ligation (B Lynch or other techniques), pelvic arteries embolization, surgical vascular ligation, administration of rFVIIa and hysterectomy. ● Need for intrauterine balloon 
 ○ Percentage of patients requiring the use of intrauterine balloon within 48 hours following the administration of IMP. ○ Time of intrauterine balloon placement. ● Maternal morbi-mortality 
 ○ Length of stay in resuscitation and/or intensive care and/or post interventional care units (PICU) and/or continuous care. ○ Duration of admission in obstetrics unit. ○ Single or multi-organ failure (SOFA score) in case of transfer to resuscitation and/or intensive care and/or PICU and/or continuous care units. ○ Death during the study. ● Biological effects of fibrinogen concentrate administration 
 ○ Evolution of blood fibrinogen level and hemoconcentration between H0 (start of IMP infusion) and D2. ● Tolerance of fibrinogen concentrate administration 
 ○ Serious and non-serious adverse events (AE).

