8.1.2. Patient Inclusion

The patient is considered as included when emergency informed consent form has been signed by the patient or a member of her family or the person of trust (see Section 8.1.1).

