8.2. Schedule of visits

The duration of patient participation is 6 ± 2 weeks starting from randomisation. After enrolment, all patients will be treated with IMP. The start of IMP administration corresponds to H0.

8.2.1. Visit 1: Inclusion / Blood sampling 1

Information on the study will be given at the moment of the diagnosis of haemorrhage (see Section 8.1.1).

- Informed consent must be obtained before any study procedure;
- Eligibility criteria check (inclusion and non-inclusion criteria);
- Date and start time of prostaglandin infusion;
- Demographics (height, weight prior to pregnancy and last known weight);
- Thromboembolic and obstetrical events and any clinically relevant medical conditions;
- Pregnancy parameters:
 - Hb level during the third trimester,
 - Hb level at the sixth month,
 - Ht and platelets will be collected if available
 - Date of last menstrual period, gestational age,
- Delivery parameters
 - Times of the start and the end of delivery;
 - Number of live births and/or stillbirths;
 - Procedures: artificial delivery, uterine or genital examination
- Prior and concomitant treatment (see Section 7) including intravenous fluids and blood products since the start of delivery;
- Haemorrhage parameters :
 - Haemorrhage start time;
 - Measured or estimated volume of blood loss at the start of prostaglandin infusion;
- Physical examination will include a comprehensive standard evaluation of all systems: cardiovascular system, respiratory system, skin and appendices, gastrointestinal system, ear-

nose-throat, lymphatic nodes, spleen, central nervous system, eyes, musculoskeletal system, endocrine system, argental system, psychiatric state. Signs for possible thrombosis will be checked.

- Vital signs:
 - Measurement of arterial blood pressure (systolic and diastolic),
 - Heart rate.
- Blood sampling for laboratory parameters at inclusion:
 - Complete blood count, Hb, Ht, platelets,
 - Haemostatic profile: fibrinogen, PT, QT, aPTT, D-dimers,
 - Blood urea and serum creatinine.

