1.10.2 Secondary endpoints

1.10.2.1 Evolution of haemorrhage

- Percentage of patients losing at least 4 g/dL of Hb within 48 hours following IMP administration with regards to the Hb reference level.
- Percentage of patients losing at least 3 g/dL of Hb within 48 hours following IMP administration with regards to the Hb reference level.
- Percentage of patients requiring the transfusion of at least 2 units of RBCs within 48 hours following IMP administration.
- Percentage of patients losing at least 4 g/dL of Hb within 48 hours following IMP administration with regards to the level of Hb measured at inclusion.
- Percentage of patients with an occurrence of Hb level < 9 g/dl within 48 hours following IMP administration.
- Number of units of transfused blood products within 48 hours following IMP administration.
- Calculated volume of total blood loss, 48 hours following IMP administration.

The calculation and adjustment of total blood loss with regards to transfusional needs will be calculated at time of statistical analysis as follows:

- Total blood loss (mL) = blood loss calculated + blood loss compensated by transfusion
- Calculated blood loss: Pregnancy total blood volume x (Ht0 – Htf) x (100/35)
 - Pregnancy total blood volume = (Maternal weight measured before pregnancy x 65 mL/kg) x 1.4
 - Ht0: last available value of haematocrit before delivery
 - Htf: value of haematocrit in the morning of D2

Blood loss compensated by transfusion (mL): n RBC x 500mL (with n corresponding to the number of transfused units and 500mL = total transfused blood volume of 300 mL RBC with Ht of 60%).

1.10.2.2 *Need for haemostatic intervention*

- Percentage of patients requiring at least one of the following interventions within 48 hours following IMP administration of: pelvic arteries embolization, surgical vascular ligation, uterine ligation (B Lynch or other techniques), administration of recombinant activated Factor VII (rFVIIa) and hysterectomy.

1.10.2.3 *Need for intrauterine balloon*

- Percentage of patients requiring the use of intrauterine balloon within 48 hours following the administration of IMP.
- Time of intrauterine balloon placement.

1.10.2.4 *Maternal morbi-mortality*

- Length of stay in resuscitation and/or intensive care and/or post interventional care units (PICU) and/or continuous care.
- Length of stay in obstetrics units.

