- The percentage of patients losing at least 3 g/dL of Hb within 48 hours following IMP administration with regards to the Hb reference level will be calculated and chi-square or Fisher exact tests will be used to compare between the Clottafact[®] group and placebo group.
- The percentage of patients with an occurrence of Hb level < 9 g/dL within 48 hours following IMP administration will be calculated and chi-square or Fisher exact tests will be used to compare between the Clottafact[®] group and placebo group.

3.3.6.3.2.2.2.2 Analyses of the number of units of transfused blood units

The number of units of transfused blood products within 48 hours following IMP administration will be calculated for the Clottafact[®] group and placebo group and compared using a Chi-square or generalized Fisher exact test.

3.3.6.3.2.2.2.3 Duration of haemorrhage

The time to the end of haemorrhage (hours) will be summarised by treatment group. The duration of the haemorrhage will be presented using Kaplan-Meier estimates to the end of haemorrhage. A log rank test will be used to compare the duration of haemorrhage curves between the Clottafact[®] group and placebo group.

3.3.6.3.2.2.3 Description of haemostatic intervention

The percentage of patients with haemorrhage leading to the occurrence of morbidity will be compared by treatment group using Fisher exact test. The percentage of patients requiring at least pelvic arteries embolization, surgical vascular ligation, uterine ligation, administration of recombinant activated Factor VII, intrauterine

ballon, and hysterectomy within 48 hours following the IMP administration will be calculated by group.

The time of intrauterine balloon placement will be described as other haemostatic interventions.

Fisher exact tests will be performed to compare the occurrence of haemostatic interventions by treatment groups.

3.3.6.3.2.2.4 Description of maternal morbidity

The maternal morbidity will be analyzed in the subgroup of patients transferred in resuscitation and/or intensive care and/or PICU and/or continuous care units with:

1. *Duration (days) in resuscitation and/or intensive care and/or PICU and/or continuous care units.*
2. *The maximal SOFA score,*
3. *Duration of admission in obstetrics room (hours), duration of hospitalization and number of days with assisted ventilation*

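### The exploratory Hb < 9 g/dL endpoint starts its 48 h window at inclusion in the protocol and at IMP administration in the SAP, the change is not listed, and the crude test ignores pre-IMP Hb

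*Protocol*

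**What the plan says.** **Protocol.** Section 10.1.2 lists "Percentage of patients with an occurrence of Hb level < 9 g/dL within the 48 hours period following inclusion"; the synopsis and section 3.2.2.1 use the same inclusion clock. The other haemorrhage endpoints in those lists run from IMP administration. Section 8.1.2 fixes the moment of inclusion: "The patient is considered as included when emergency informed consent form has been signed". Section 8.2.1 requires that "Informed consent must be obtained before any study procedure", and Visit 1 then contains "Blood sampling for laboratory parameters at inclusion", with Hb among the tests. The flow-chart places Visit 1 before H0, which is the start of IMP infusion.

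**SAP.** Section 1.10.2.1 lists "Percentage of patients with an occurrence of Hb level < 9 g/dl within 48 hours following IMP administration". Section 3.3.6.3.2.2.2.1 repeats that clock ("The percentage of patients with an occurrence of Hb level < 9 g/dL within 48 hours following IMP administration will be calculated") and names a chi-square or Fisher exact test between arms. The table of changes in section 2.2 has no entry for the moved clock.

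**Status.** The endpoint is not one of the three key secondary variables in SAP 3.3.6.3.1. It lies outside the Hochberg procedure, and SAP 3.3.6.3.2.2 treats it as exploratory.

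**The concern.** The endpoint sits under evolution of haemorrhage and is meant to describe what happens after treatment. Two features work against that.

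First, under the protocol wording a value measured before the IMP can itself be the event. Under the SAP wording it cannot. Analysts following the two documents could report different counts for the same listed endpoint, with no declared change to say which applies.

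Second, neither document uses a woman's pre-IMP Hb in this comparison. The only Hb exclusion concerns the third trimester (below 10 g/dL, Protocol 5.2.2), before the bleeding. The SAP itself expects falls before the IMP: a loss of at least 2 g/dL at Visit 1 is a named baseline covariate for the primary endpoint (SAP 3.3.6.1.2). A woman with a reference Hb of 10.5 g/dL and that loss is at 8.5 or lower before H0. The transfusion objective in Protocol 7.2 is Hb of at least 8 g/100 ml, so a value between 8 and 9 already meets it, and a post-H0 value below 9 is then likely. A crude test treats such a woman like one who starts at 11.

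**Working it through.** **1. The two clocks side by side.**

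| | Protocol synopsis, 3.2.2.1, 10.1.2 | SAP 1.10.2.1, 3.3.6.3.2.2.2.1 |
|---|---|---|
| Window opens | consent signature | IMP administration (H0) |
| Visit 1 Hb below 9 | counts as an event | does not count |
| Post-H0 Hb below 9 | counts | counts |
| Use of pre-IMP Hb | none | none |

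The counts differ only for women below 9 at Visit 1 whose later values in the window are all 9 or above. Their number is not in the documents.

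**2. The plan's own figure.** The documents give no rate, power or sample size for this endpoint. The nearest figure is the primary sample size (Protocol 12.3): 42% vs 27%, two-sided 5%, 90% power, unpooled Z test.

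n = (1.960 + 1.282)² × (0.42×0.58 + 0.27×0.73) / 0.15² = 205.8, rounded up to 206 per arm, as stated.

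**3. Illustration of the loss.** Inputs:
- n: SAP 1.11 gives 448 recruited and 1.55% excluded, so 448 × 0.9845 = 441, about 220 per arm.
- Rates among women at or above 9 before the IMP: 42% and 27%, borrowed from the primary endpoint (assumption).
- Share q already below 9: unknown, shown from 5% to 30% (assumption).
- Women already below 9 are all events after H0 in both arms (assumption, relaxed in step 4).

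Observed rate = q + (1 − q)p, so the observed difference is (1 − q) × 15 points. Power is Φ[(d − 1.96·SE₀)/SE₁], with SE₀ from the pooled rate and SE₁ from the separate rates. The comparison column uses 220 × (1 − q) women per arm at 42% vs 27%.

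| q | Rates, all women | Difference | Power, all women, crude | Power, women at or above 9 |
|---|---|---|---|---|
| 0% | 42.0 vs 27.0 | 15.0 | 91% | 91% |
| 5% | 44.9 vs 30.7 | 14.2 | 87% | 90% |
| 10% | 47.8 vs 34.3 | 13.5 | 82% | 88% |
| 20% | 53.6 vs 41.6 | 12.0 | 71% | 84% |
| 30% | 59.4 vs 48.9 | 10.5 | 60% | 79% |

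With 57.5% vs 42.5% instead, power is 81% against 85% at q = 10%, and 73% against 81% at q = 20%.

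In this extreme case a comparison stratified on pre-IMP status draws all its information from women at or above 9. The last column therefore indicates roughly what using baseline status can recover. The gain from adjusting for Hb as a continuous variable depends on a distribution that the documents do not give.

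**4. Persistence.** If only 80% of women already below 9 have a post-H0 value below 9, equally in both arms, the difference is still (1 − q) × 15 points. Power moves by less than one point (82.9% against 82.3% at q = 10%).

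**5. Chance imbalance.** The standard deviation of the difference between arms in the share already below 9 is √[2q(1 − q)/220]. At q = 10% this is √(0.18/220) = 2.9 points. With no treatment effect and an at-risk rate of 42%, an imbalance of that size moves the crude difference by 2.9 × (1 − 0.42) = 1.7 points. The crude test's standard error allows for this variation; adjustment would remove much of it.

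**The case against.** **The SAP specifies the analysis, and its clock already removes the Visit 1 sample.** This stands. A reader might infer that the conflicting clocks cause the attenuation, and they do not. The clocks decide only whether the Visit 1 value counts. The attenuation comes from women whose pre-IMP Hb makes a post-H0 value below 9 likely under either clock. Where that persistence is high, the two clocks also give nearly the same count.

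**The percentage among all women is a legitimate estimand.** This also stands. The proportion of treated women with a post-H0 Hb below 9 is estimated without bias, and (1 − q) times the at-risk difference is the true effect in that population. Restricting to women at or above 9 is a choice of estimand, not the repair of an error, and it drops the most anaemic women.

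**Hb after treatment is covered elsewhere.** The SAP analyses the evolution of Hb at H2, H6 and D2 by a mixed model under a change-from-baseline heading (3.3.6.3.2.2.1). That answers a related question. It does not settle which clock defines this endpoint.

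**The size is assumed.** Correct: neither q nor the rates are documented.

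**A neighbouring endpoint.** A reader might also infer that the loss of at least 4 g/dL from the inclusion Hb has been dropped, because SAP 3.3.6.3.2.2.2.1 gives it no bullet. SAP 3.3.6.3.1 takes in all of 1.10.2, Table 14.2.6.2.3.1 covers the evolution of haemorrhage, and Protocol 12.10.1.3.2 supplies a default chi-square test. Only explicit detail is missing.

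**Conclusion.** The clock conflict and its absence from SAP 2.2 are matters of text and certain. The disregard of pre-IMP Hb in this comparison is also plain. Its consequence is lost precision and a result more exposed to chance baseline imbalance.

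It would be wrong to read this as bias towards one arm or as type I error inflation: randomisation balances pre-IMP Hb in expectation, and the crude test is valid.

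The magnitude cannot be established from the documents. Under the illustrative rates, the gap between the crude all-women comparison and one confined to women at or above 9 is about 3 power points if 5% were already below 9 (87% against 90%) and about 13 if 20% were (71% against 84%). Those figures assume borrowed event rates, an assumed share, and no treatment effect among women already below 9.

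The endpoint is exploratory, so neither the primary analysis nor the three key secondary tests are affected. This is a modest point with a nearly costless repair.

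**What to change.** 1. In Protocol 3.2.2.1, 10.1.2 and the synopsis, start the window at H0 as the SAP does, and say in both documents that only samples taken after H0 count.
2. Add the changed clock, with its reason, to SAP 2.2.
3. In SAP 3.3.6.3.2.2.2.1, keep all women and replace the crude test for this endpoint with a logistic regression on treatment and pre-IMP Hb. Enter Hb as a continuous variable: if every woman already below 9 is an event, a below-9 indicator has no finite estimate. Baseline is already defined as the last value before IMP infusion (SAP 3.3.5.3); state what is done when the Visit 1 Hb is missing, since that rule could otherwise fall back on a pregnancy value.
4. Show by arm the number of women already below 9 before the IMP, beside the raw percentages.
5. Optionally, add new occurrence among women with pre-IMP Hb of 9 or more as a supplementary analysis. Selection is on a pre-treatment value, so the randomised comparison is preserved.

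Cost: a few lines of wording and code, using data already collected. The main result becomes a conditional odds ratio rather than a comparison of crude percentages, which is slightly harder to read; the raw percentages in step 4 offset that.

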10.2. Assessment of Safety

AEs and SAEs from all patients followed throughout the study will be recorded and reported, as described in [Section 9.5](#), whether or not the AE was determined to be related to the administration of IMP.

Safety evaluation will include the monitoring of the following items:

- Physical examination performed at inclusion and hospital discharge;
- Vital signs (blood pressure and heart rate) will be monitored at inclusion visit, randomisation, H2, H6, discharge from the obstetrics room, morning of D2, intensive care unit discharge (if applicable) and hospital discharge.
- Tolerance of fibrinogen concentrate administration
 - Serious and non-serious adverse events (AE)
 - Symptomatic thromboembolic events within the 6 weeks following the administration of IMP.

In this study, all events related to PPH (anaemia, progressing or worsening of haemorrhage) will not be reported as AEs as they are already reported as efficacy criteria.

- Laboratory parameters:
 - Change in creatinine and urea between inclusion and D2
 - Change in TP, aPTT, D-dimers, platelets between inclusion and each determination times.

